4.8.4. Safety Management for ATRA Combination

4.8.4.1. Retinoic Acid syndrome

About 25% of patients with APL treated with ATRA have experienced the retinoic acid-(RA) syndrome characterized by fever, dyspnea, acute respiratory distress, weight gain, radiographic pulmonary infiltrates, pleural and pericardial effusions, edema, and hepatic, renal, and multi-organ failure [ATRA Prescribing Information, 2004]. This syndrome has occasionally been accompanied by impaired myocardial contractility and episodic hypotension. The syndrome generally occurs during the first month of treatment, with some cases reported following the first dose of ATRA.

Retinoic Acid Syndrome should be strongly suspected if the following signs or symptoms (without any other clear or established etiology) emerge during treatment with GSK2879552:

- New or worsening progressive dyspnea or hypoxemia, with increasing demands for supplemental oxygen; respiratory distress refractory to treatment for the initially suspected cause
- Radiologic evidence of new or worsened bilateral pulmonary involvement (infiltrates or opacities) with or without presence of infection, refractory to treatment with anti-infectives (antibiotics, antivirals, antifungals)
- Radiologic evidence of new or worsened pleural or pericardial effusion that is refractory to treatment for an initially suspected cause
- New or worsened peripheral edema, with rapid weight gain (e.g., >5 kg/11 pounds over 7 days)
- Increase in serum creatinine (e.g., >2-fold from baseline)
- The following symptoms or signs may be features of retinoic acid syndrome but if isolated and not accompanied by pulmonary or renal manifestations, may not require rapid initiation of retinoic acid syndrome treatment (unless sufficiently severe and prolonged):
 - Unexplained fever $\geq 38^{\circ}\text{C}$ (100.4°F)
 - Rash of unknown origin
 - Bone pain

- Lymphadenopathy

The measures below are recommended to be taken at the earliest manifestations of suspected retinoic acid syndrome:

- Patients with severe or rapidly progressing retinoic acid syndrome should be hospitalized for continued observation
- In case of uncertainty with the diagnosis, e.g., presence of less specific symptoms of moderate severity, patients should be closely monitored, as the condition may rapidly worsen
- Corticosteroids should be promptly initiated (e.g., 10 mg of dexamethasone every 12 hours until resolution of retinoic acid syndrome). Once resolved the corticosteroid dose can be progressively reduced over 1-2 weeks
- GSK2879552 and/or ATRA may be withheld at the physician's discretion. Due to the long half-life of GSK2879552 (about 16 hours), treatment interruption may not immediately reverse the symptoms of retinoic acid syndrome. If interrupted, GSK2879552 treatment may be reinitiated at the original or a reduced dose, once the signs and symptoms resolve and the patient's clinical condition improves
- In patients with elevated WBC counts, prompt initiation of hydroxyurea is suggested, or treated as per standard local practice (e.g., dose of 2 to 3g PO 2- or 3-times daily for WBC $>30 \times 10^9/L$)
- In cases of severe leukocytosis, use of leukapheresis may be appropriate
- For substantial fluid accumulation, initiation of furosemide may be appropriate, as per local standard practice
- Patients with pericardial effusion (a less common manifestation of retinoic acid syndrome) can require urgent cardiac intervention due to it being a life-threatening condition
- Patients with increasing serum creatinine levels should be evaluated for tumor lysis syndrome
- Patients experiencing a rapid increase in peripheral blood cells should be monitored for disseminated intravascular coagulopathy and hemorrhage
- Imaging techniques such as standard or high-resolution computerized tomography (CT) scan and chest X-ray are useful for establishing a diagnosis of retinoic acid syndrome by identifying pulmonary infiltrates or effusions; noting that a CT scan is more sensitive in detecting early radiological signs of retinoic acid syndrome-associated changes

4.8.4.2. Liver Function Test Elevation

If ALT \geq 5 X ULN, ATRA dose should be held while GSK2879552 dosing continues

- If resolved in 14 days, ATRA dose should resume at full dose
- If not resolved in 14 days, GSK2879552 dose should be also held.
 - If resolved in another 14 days, resume GSK2879552 at a reduced dose by minimum 25% and ATRA at full dose
 - If not resolved in another 14 days, withdraw the subject from the study.

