4.7. Safety Management Guidelines

4.7.1. Liver Chemistry Stopping Criteria

Liver chemistry threshold stopping criteria have been designed to assure subject safety and to evaluate liver event etiology during administration of study treatment(s) and the follow-up period. Study treatment(s) will be stopped if any of the following liver chemistry stopping criteria is/are met:

1. Alanine aminotransferase (ALT) ≥ 5 X (times) upper limit of normal (ULN) and bilirubin ≥ 2 Xs ULN (or ALT ≥ 5 X ULN and international normalization ratio [INR] > 1.5)

NOTE: Serum bilirubin fractionation should be performed if testing is available. If fractionation is unavailable, urinary bilirubin is to be measured via dipstick (a measurement of direct bilirubin, which would suggest liver injury).

2. ALT ≥ 8 X ULN.
3. ALT ≥ 5 X ULN if associated with the appearance or worsening of rash or hepatitis symptoms (fatigue, nausea, vomiting, right upper quadrant pain or tenderness, or jaundice) or hypersensitivity (such as fever, rash or eosinophilia).
4. ALT ≥ 5 X ULN persists for ≥ 4 weeks.
5. ALT ≥ 5 X ULN and cannot be monitored weekly for 4 weeks.

Subjects with ALT ≥ 5 X ULN **and** < 8 Xs ULN **and** bilirubin < 2 X ULN, who do not exhibit hepatitis symptoms or rash, can continue study treatment(s) as long as they can be monitored weekly for 4 weeks. See following section for details on weekly follow-up procedures for these subjects.

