4.7.1.1. Liver Chemistry Follow-up Procedures

Refer to the diagram in [Appendix 5](#) for a visual presentation of the procedures listed below.

The procedures listed below are to be followed if a subject meets the liver chemistry stopping criteria defined in Section [4.7.1](#):

- Immediately withdraw the subject from study treatment.

- Notify the GSK Medical Monitor within 24 hours of learning of the abnormality to confirm the subject's study treatment(s) cessation and follow-up.
- Complete the "Safety Follow-Up Procedures" listed below.
- Complete the liver event electronic case report forms (eCRFs). If the event also meets the criteria of a serious adverse event (SAE) (see Section 8.2), the SAE data collection tool will be completed separately with the relevant details.
- Restart or rechallenge of study treatment requires approval as described in Section 9.

Safety Follow-Up Procedures for subjects with ALT ≥ 3 times ULN:

- Monitor subjects **weekly** until liver chemistries (ALT, aspartate aminotransferase [AST], alkaline phosphatase [ALP], and bilirubin) resolve, stabilize or return to within baseline values.

Safety Follow-Up Procedures for subjects with ALT ≥ 5 times ULN and bilirubin ≥ 2 times ULN (or ALT ≥ 5 times ULN and INR > 1.5):

- **This event is considered an SAE** (see Section 8.2). Serum bilirubin fractionation should be performed if testing is available. If fractionation is unavailable, urinary bilirubin is to be measured via dipstick (a measurement of direct bilirubin, which would suggest liver injury).
- Make every reasonable attempt to have subjects return to the clinic within 24 hours for repeat liver chemistries, additional testing, and close monitoring (with specialist or hepatology consultation recommended).
- Monitor subjects **twice weekly** until liver chemistries (ALT, AST, alkaline phosphatase, bilirubin) resolve, stabilize or return to within baseline values.

In addition, for all subjects with ALT ≥ 5 times ULN, every attempt must be made to also obtain the following:

- Viral hepatitis serology including:
 - Hepatitis A Immunoglobulin M (IgM) antibody.
 - Hepatitis B surface antigen and Hepatitis B Core Antibody (IgM).
 - Hepatitis C ribonucleic acid (RNA).
 - Cytomegalovirus IgM antibody.
 - Epstein-Barr viral capsid antigen IgM antibody (or if unavailable, obtain heterophile antibody or monospot testing).

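### The ATRA-arm liver rule (Protocol 4.8.4.2) continues GSK2879552 at any ALT ≥5×ULN, including cases where the general stopping rule (4.7.1) withdraws study treatment

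*Protocol*

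**What the plan says.** Protocol Section 4.7.1 applies to all subjects, with no exception for the ATRA arm: "Study treatment(s) will be stopped if any of the following liver chemistry stopping criteria is/are met". The five criteria are:

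1. ALT ≥5×ULN with bilirubin ≥2×ULN, or with INR >1.5.
2. ALT ≥8×ULN.
3. ALT ≥5×ULN "if associated with the appearance or worsening of rash or hepatitis symptoms (fatigue, nausea, vomiting, right upper quadrant pain or tenderness, or jaundice"), or hypersensitivity, for which fever, rash and eosinophilia are given as examples.
4. ALT ≥5×ULN lasting 4 weeks or more.
5. ALT ≥5×ULN where weekly monitoring for 4 weeks is not possible.

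Treatment may go on only at ALT ≥5 to <8×ULN with bilirubin <2×ULN, in subjects "who do not exhibit hepatitis symptoms or rash, can continue study treatment(s) as long as they can be monitored weekly for 4 weeks".

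Once a criterion is met, Section 4.7.1.1 requires the site to "Immediately withdraw the subject from study treatment". Section 9 then bars restart without the sponsor's medical governance approval, ethics approval where required, and a separate signed consent.

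Section 4.8.4.2, for the ATRA combination, is triggered by ALT ≥5×ULN alone: "ATRA dose should be held while GSK2879552 dosing continues". Its next steps are:

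- "If resolved in 14 days, ATRA dose should resume at full dose".
- If ALT has not resolved by day 14, GSK2879552 is held too.
- If ALT resolves in the following 14 days, GSK2879552 returns with a reduction of at least 25% and ATRA returns at full dose.
- If it does not, the subject is withdrawn.

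**The concern.** Every subject who meets a 4.7.1 criterion also has ALT ≥5×ULN, and so also triggers 4.8.4.2. For the same ATRA-arm subject on the same day, one section can require withdrawal while the other says to keep dosing GSK2879552. The arm-specific section is the one a site is likely to turn to, and it names each drug. Section 4.7.1 refers only to study treatment, a term that Section 5 allows to mean either drug or the combination.

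What is at stake is continued dosing, or restart without safeguards, during a possible drug-induced liver injury. Of criterion 1 the protocol itself says "This event is considered an SAE", and Section 9.1 cites 13% mortality on rechallenge after such injury. Section 1.3.4 gives GSK2879552 an average terminal half-life of 12 to 38 hours, so a dose given in error does not clear quickly.

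**Working it through.** No sample size, power or error rate is involved, so the check sets the two rules side by side. Day 0 is the day on which ALT ≥5×ULN and the criterion are first met.

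| 4.7.1 criterion | 4.7.1 stops on | Literal 4.8.4.2 | Result |
|---|---|---|---|
| 1. bilirubin ≥2×ULN or INR >1.5 | day 0 | GSK2879552 continues | conflict |
| 2. ALT ≥8×ULN | day 0 | GSK2879552 continues | conflict |
| 3. rash, hepatitis symptoms, hypersensitivity | day 0 | GSK2879552 continues | conflict |
| 4. ALT ≥5×ULN for ≥4 weeks | day 28 | held from day 14, withdrawn at 14 + 14 = 28 | no conflict |
| 5. weekly monitoring not possible | day 0 | GSK2879552 continues | conflict |

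Four of the five conflict. Under criterion 4, 4.8.4.2 is the earlier rule by 28 − 14 = 14 days.

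For a subject who meets a conflicting criterion, literal 4.8.4.2 has three outcomes:

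- **Resolved by day 14.** GSK2879552 is never interrupted, and ATRA returns at 100%.
- **Resolved between day 15 and day 28.** There are 14 − 0 = 14 days of GSK2879552 beyond the 4.7.1 stop. Then GSK2879552 returns at no more than 100% − 25% = 75% and ATRA at 100%.
- **Unresolved at day 28.** There are 14 extra days of GSK2879552, then withdrawal.

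GSK2879552 continues past the 4.7.1 stop in all three. Drug is returned without Section 9 in two of three: ATRA only in the first, both drugs in the second. These are branches of a rule, not probabilities.

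Section 1.3.6.1 shows that criterion 3 signs are expected in this arm. Among ATRA-treated patients it reports fever in 83%, nausea/vomiting in 57% and rash in 54%. Joint rates are not given, so only bounds are available:

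- At least one of the three: lower bound max(83, 57, 54) = 83%; upper bound min(100, 83 + 57 + 54 = 194) = 100%.
- Nausea/vomiting or rash only: lower bound max(57, 54) = 57%; upper bound min(100, 57 + 54 = 111) = 100%.

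Both ranges are any-time rates. The documents do not give the share of patients with these signs at the same time as ALT ≥5×ULN, so neither range measures how often the conflict would arise.

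**The case against.** The strongest reply is that the protocol as a whole already ranks the rules. Section 4.7.1 is mandatory, while 4.8.4.2 says what should be done and sits under a heading of guidelines for managing common toxicities. Section 6.3 makes meeting a 4.7.1 criterion an end of treatment, Section 9 bars restart after one, and the ATRA risk table in 1.4.5.1 presents the stopping criteria and the management guideline as both in force. A harmonious reading exists: 4.8.4.2 governs only the zone where 4.7.1 allows treatment to continue, and there it is the stricter rule.

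There is also a safeguard. Section 4.7.1.1 tells the site to "Notify the GSK Medical Monitor within 24 hours of learning of the abnormality", and the stated purpose is to confirm that treatment has stopped. Section 8.5.2 sets the same 24 hours for its listed ALT ≥5×ULN categories. Fourteen extra days would therefore need both site and sponsor to overlook 4.7.1. Criterion 5 should be rare, because weekly tests are already required from ALT ≥3×ULN. The fever rate should carry little weight, since criterion 3 lists fever only as an example of hypersensitivity. Reading a stop of study treatment as one drug only is also strained, because 4.7.1 allows for the plural.

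Most of this stands as evidence of intent and as a limit on how long an error would last. It does not supply the missing text. The ranking has to be inferred from several sections, 1.4.5.1 names both rules without ordering them, and 4.8.4.2 contains nothing that confines it to the compatible zone. Notification shortens an error but does not tell the site what to do with the next daily dose.

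**Conclusion.** The inconsistency is real. As written, 4.8.4.2 contradicts 4.7.1 and 4.7.1.1 under criteria 1, 2, 3 and 5, and contradicts Section 9 on restart in two of its three outcomes. At ALT ≥5 to <8×ULN with no other feature, the two rules are compatible.

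The conclusion rests on a literal reading of 4.8.4.2. The liver diagram in Appendix 5 is not visible in the text available, so whether it settles precedence could not be checked. How often the conflict would occur cannot be estimated from the documents. SAP Section 2.1 records that the study ended early and Part 2 was never opened, which limits further exposure but does not make the rules consistent.

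This should be corrected on patient-safety grounds, with high confidence. It affects no sample size, error rate or planned analysis.

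**What to change.** Add two sentences to Section 4.8.4.2:

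- The section applies only when ALT is ≥5 and <8×ULN, bilirubin is <2×ULN, INR is ≤1.5 if measured, there are no hepatitis symptoms, rash or hypersensitivity, and weekly monitoring is possible.
- If any 4.7.1 stopping criterion is met, both GSK2879552 and ATRA are stopped, and Sections 4.7.1, 4.7.1.1 and 9 take precedence over 4.8.4.2.

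Naming both drugs also removes the ambiguity in the term study treatment. The cost is this text change alone; design, sample size and analysis are unaffected.

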4.8.4.3. Pseudotumor Cerebri (benign intracranial hypertension)

Early signs and symptoms include papilledema, headache, nausea, vomiting, and visual disturbances. Subjects with these symptoms should be evaluated for pseudotumor cerebri, and, if present, appropriate care should be instituted including high dose steroid. ATRA dose should be held for moderate to severe pseudotumor cerebri.

5. INVESTIGATIONAL PRODUCT(S)

The term ‘study treatment’ is used throughout the protocol to describe investigational product(s) (IP) received by the subject as per the protocol design. Study treatment may therefore refer to the individual study treatments or the combination of those study treatments.

5.1. Description of Investigational Product(s)

Product name:	GSK2879552 Capsule
Formulation description*:	GSK2879552 capsules contain 0.5 mg, 2 mg or 5 mg of GSK2879552 as parent.
Dosage form:	Capsule
Unit dose strength(s)	0.5 mg, 2 mg and 5 mg
Route/ Regimen	Oral The initial dosing regimen will be continuous oral daily dosing. Subjects should take their doses fasted with approximately 200 mL of water.
Physical description:	0.5 mg GSK2879552: Opaque Size 1 capsule composed of a light green body and a light green cap with no identifying markings containing a white to slightly coloured powder. 2 mg GSK2879552: Opaque Size 1 capsule composed of a pink body printed with two black lines and a pink cap printed with two black lines, containing a white to slightly coloured powder. 5 mg GSK2879552: Opaque Size 1 capsule composed of a Swedish Orange body and a Swedish Orange cap with no identifying markings containing a white to slightly coloured powder.

* NOTE: 0.25 mg strength of GSK2879552 capsule is no longer being used and is removed from the table.

GSK2879552 will be provided to sites by GSK, whereas ATRA will be locally supplied and prepared according to local standards. The contents of the label will be in accordance with all applicable regulatory requirements.

Product name:	Tretinoin (ATRA) Capsule
Formulation description:	ATRA is supplied as a 10 mg capsule for oral administration.
Dosage form:	Capsule
Unit dose strength(s)	10 mg
Route/Regimen	Oral/The initial dosing regimen will be continuous oral twice daily dosing, i.e., morning and evening. ATRA dose may be divided evenly 2-4 times a day, as needed. Subjects should take their morning dose fasted, at the same time as GSK2879552. If ATRA concentrations are lower than anticipated following fasted administration, subjects may be asked to take their morning ATRA dose with food. Subject can take their evening ATRA dose with food.

5.2. Preparation/Handling/Storage of Investigational Product

Handling

Under normal conditions of handling and administration, investigational product (IP) is not expected to pose significant safety risks to site staff. A Material Safety Data Sheet (MSDS) describing the occupational hazards and recommended handling precautions will be provided to site staff if required by local laws or will otherwise be available from GSK upon request.

In the case of unintentional occupational exposure notify the study monitor, the GSK Medical Monitor and/or the study manager.

Refer to the Study Procedures Manual (SPM) for detailed procedures for the disposal and/or return of unused study treatment(s).

Storage

GSK2879552 must be stored in a secure area under the appropriate physical conditions for the product. Access to and administration of the GSK2879552 will be limited to the investigator and authorized site staff. GSK2879552 must be dispensed or administered only to subjects enrolled in the study and in accordance with the protocol.

GSK2879552 is to be stored at a temperature range of 2-8°C (36-46°F), protected from moisture. See package insert for ATRA storage conditions.

Maintenance of a temperature log (manual or automated) is required at the clinical sites.

5.3. Product Accountability

In accordance with local regulatory requirements, the investigator, designated site staff, or head of the medical institution (where applicable) must document the amount of investigational product (IP) dispensed and/or administered to study subjects, the amount returned by study subjects, and the amount received from and returned to GSK, when applicable. Product accountability records must be maintained throughout the course of the study. Refer to the Study Procedures Manual (SPM) for further detailed instructions on product accountability.

5.4. Treatment Compliance

On clinic days, GSK2879552 and ATRA should be taken in the clinic after safety procedures including blood sampling for CBC and PK/PD samplings, if applicable, are completed. When subjects self-administer study treatment(s) at home, subjects will be instructed to record time and date of dosing in the supplied GSK dosing diary.

Compliance with IP will be assessed through querying the subject during the site visits and reviewing the dosing diary, and documented in the source documents and eCRF. A record of the number of capsules dispensed to and taken by each subject must be maintained and reconciled with study treatment and compliance records. Treatment start and stop dates, including dates for treatment delays and/or dose reductions will also be recorded in the eCRF.

5.5. Treatment of Investigational Product Overdose

In the event of an overdose (defined as administration of more than the protocol-specified dose) of GSK2879552, the investigator should:

- contact the GSK Medical Monitor immediately
- closely monitor the subject for AEs/SAEs and laboratory abnormalities at least 7 days
- document the quantity of the excess dose as well as the duration of the overdosing in the eCRF.

The MTD of ATRA in patients with myelodysplastic syndrome or solid tumors was 195mg/m²/day. Overdosage with other retinoids has been associated with transient headache, facial flushing, cheilosis, abdominal pain, dizziness and ataxia. These symptoms have quickly resolved without apparent residual effects. There is no specific treatment in the case of an overdose, however, it is important that the patient be treated in a special hematological unit [ATRA Prescribing Information, 2004].

Decisions regarding dose interruptions or modifications will be made by the investigator in consultation with the GSK Medical Monitor based on the clinical evaluation of the subject.

6. COMPLETION OR WITHDRAWAL OF SUBJECTS

6.1. Screen and Baseline Failures

Screen failures are defined as subjects who consent to participate in the clinical trial but are never subsequently randomized. In order to ensure transparent reporting of screen failure subjects, meet the Consolidated Standards of Reporting Trials (CONSORT) publishing requirements, and respond to queries from Regulatory authorities, a minimal set of screen failure information is required including Demography, Screen Failure details, Eligibility Criteria, and any Serious Adverse Events.

Individuals who do not meet the criteria for participation in this study (screen failure) may be rescreened. Rescreened participants should be assigned the same participant number as for the initial screening if rescreening for same arm of study (monotherapy to monotherapy or ATRA combination to ATRA combination.) If rescreening for a different arm of the study, (monotherapy to ATRA combination or ATRA combination to monotherapy) participants will need a new screening number. Please refer to the Study Procedures Manual for more details.

6.2. Subject Completion Criteria

In Part 1, a subject will be considered to have completed the study if:

- they complete screening assessments, the 28-day DLT observation period, and taking a minimum of 75% of planned doses,
- they progress or die while receiving study treatment, or
- they are receiving ongoing study treatment at the time of the Sponsor's decision to close the study.

In Part 2, a subject will be considered to have completed the study if:

- they die while receiving study treatment,
- they progress while receiving study treatment and are followed until death, or
- they are receiving ongoing study treatment at the time of the Sponsor's decision to close the study.

Subjects who have not died, and are no longer being followed for survival are considered to have discontinued the study. The End of Study eCRF should only be completed when a subject is no longer being followed.

